The study Investigators (or designee) participating in the safety run-in of applicable cohorts and the Sponsor clinical team members will constitute the Study Board (SB). The SB will review clinical data on a regular basis. In order to decide dose confirmation or dose reduction on the basis of their knowledge of the safety data. Minutes of each meeting will be written by the Sponsor and distributed to all sites participating in the safety run-in. Decisions regarding final dose selection will be made during one of the SB meetings and documented in the meeting minutes.

After safety run-in dose confirmation, occurrence of any treatment related G3 or higher AE (excluding lymphocyte count decrease) not resolving within 72 hours in $>25\%$ of participants per regimen will trigger an ad hoc Data Monitoring Committee (DMC) to rapidly convene to assess safety or need to pause enrollment to allow for a safety review. The SB (during safety run-in), independent DMC (during core phase and expansion) and Sponsor can decide to stop any cohort in the event excessive toxicity (for example but not limited to excessive irAE or excessive number of G4/5 events) is observed.

Special considerations pertaining to methodology

Interactive Response Technology will be used to control recruitment, assignment per site and facilitate the handling, management, and accountability of drug supply.

The duration of the study for a participant will include:

- **Screening period:** Up to 28 days.
- **Treatment Period:** Enrolled participants will receive continuous treatment until PD, unacceptable adverse event (AE), or other full permanent discontinuation criteria as described in [Section 7](#), or completion of the maximum cycles allowed in the substudies. However, treatment beyond PD may be allowed for up to 9 weeks if the participant appears to be benefiting clinically after discussion with the Sponsor.
- **End of Treatment and Follow-up:** End of Treatment Visit will occur 30 days ± 7 days from last IMP administration or prior to initiation of further therapy. Participants will then enter the **Observation period** and will be followed differently depending on the reason leading to **End of Treatment (EOT)**:
 1. Participants who discontinue study treatment **without PD** or who **complete** the maximum cycles allowed in the substudies **without PD** (per Lugano response criteria 2014[2]), will be followed every 3 months ± 7 days from last IMP administration, for

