safety (as per Schedule of Activities [SoA] in the individual substudy) and tumor imaging assessments, until PD, start of another anticancer therapy, final cohort cut-off, whichever comes first, before moving to the Survival Phone Call Follow-Up Period.

2. Participants who discontinue study treatment **with PD** (per Lugano response criteria 2014[2]) will be followed for safety in the Follow-Up Visit 1 occurring 3 months ± 7 days from last IMP administration, before moving to the Survival Phone Call Follow-Up Period.

Participants who move into the **Survival Phone Call Follow-up Period** will be contacted by telephone every 3 months ± 14 days to assess for survival status. Updated survival status may be requested by the Sponsor at any time during the study. Survival Phone Call Follow up will continue until death, participant request to discontinue from follow-up, or cut-off date for final analysis has been reached, or upon cancellation of Survival follow-up at the discretion of the Sponsor at any prior timepoint.

After the cohort cut-off date for the primary analysis, participants can continue to receive IMP, if clinical benefit is observed, until full permanent discontinuation criteria described in [Section 7](#) are met and will continue to undergo all assessments as per the study schedule of activities in the individual substudy.

For each cohort, the cut-off date for the final analysis (ie, analysis of secondary objectives and update of the primary objective) will be 3 years from cohort last participant in (LPI).

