The initial tumor imaging FDG-PET CT and/or MRI will be performed within 28 days prior to C1D1. Scans performed as part of routine clinical management are acceptable for use as the screening scan if they are of diagnostic quality and performed within 28 days prior to the date of enrollment. On study imaging will be performed every 9 weeks (63 ± 7 days) after the date of first IMP and if clinically indicated. FDG-PET must be performed for the 9-week and 18-week on-treatment assessments. Imaging studies should follow calendar days and should not be adjusted for delays in cycle starts or extension. The same imaging technique should be used in a participant throughout the trial. After Week 45 tumor imaging should be performed every 12 weeks (84 ± 7 days) until progressive disease (PD). Brain CT/MRI will be performed if clinically indicated.

PET imaging is always required to confirm the first documented complete response (CR). If the first documented radiological CR is seen on CT scan only, a confirmatory PET scan (either FDG PET or PET-CT) should be obtained within 14 days to confirm that timepoint's response of CR. If the PET scan is not obtained within 14 days, the timepoint must be assessed as a PR, and the next scan should be done by one of the 3 methods above as soon as possible to confirm the CR. Once CR has been established by PET imaging, subsequent CR and/or PD may be followed by CT imaging only. The CT component of the PET-CT may be used in lieu of a standalone CT/MRI, only if the CT component is of similar diagnostic quality as a contrast enhanced CT performed without PET. If contrast enhanced PET-CT with diagnostic CT is not available, a standard FDG-PET must be performed, and a standalone diagnostic CT/MRI should be performed in addition to the FDG-PET scan. If independent CT and PET scanners are used, and the participant is receiving both scans on the same day, the PET must be performed prior to the CT with IV contrast so as to not compromise PET results. The PET-CT acquisition methodology (eg, administration of intravenous contrast) should remain consistent at all imaging visits for any given patient.

Bone marrow sample is mandated to confirm CR if bone marrow was involved by lymphoma or involvement is unknown prior to study treatment and as “clinically indicated” and “If bone marrow biopsy is not negative, a radiographic timepoint response (TPR) of CR at that time point would be downgraded to an overall PR”.

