Progressive disease (PD) by CT scan, with complete metabolic response (CMR) or partial metabolic response (PMR) by PET, should be reported as PD. Although the results of PET/CT are generally prioritized over CT, CT evidence of progressive disease cannot be discounted in the overall response assessment. Additionally, the Lugano PET/CT criteria for CMR and PMR require absence of new lesions. CT may, for example, reveal progressive disease in non-measurable or non-FDG avid sites (eg, ascites, bony lesions, effusions, bowel lesions). Such cases should be reported as PD. Likewise, a CT finding of progressive disease, in the context of no metabolic response on PET, is to be considered overall disease progression, rather than stable disease.

The findings of clinical (non-radiographic) progressive disease (PD) per Investigator should be considered PD:

- Clinical suspicion of disease progression at any time requires a physical examination and imaging assessments to be performed promptly rather than waiting for the next scheduled imaging assessment.
- If skin lesions are identified as a result of a physical exam, these are to be documented via the Lugano classification 2014 assessment as a physical exam, skin lesion.

Skin lesions must be histologically confirmed for lymphoma involvement and photographed including a ruler (color photography using digital camera). Response assessment of skin lesions should be performed at baseline and at the time of each radiological assessment.

Table 4 - Imaging or disease assessment collection plan

Procedure	Screening	Post-administration assessment
Bone marrow biopsy	-	As clinically indicated during the treatment period, EOT, and Follow-visit 1 ^a
Spleen measurement by PET-CT	Mandated	As clinically indicated during the treatment period, at EOT visit and Follow-up visit 1
CT/MRI (chest, abdomen, pelvis and any other locations with suspicion or evidence of disease involvement)	Mandated	Every 9 weeks and if clinically indicated until Week 45, and every 12 weeks from Week 45 until progressive disease
Brain imaging	If clinically indicated	-
FDG-PET	Mandated	As clinically indicated during the treatment period, at EOT visit and Follow-up visit 1, and must be performed for the 9-week and 18-week on-treatment assessments.

^a A reported response of CR by CT, or CMR by FDG-PET, must be confirmed by a bone marrow assessment performed within 14 days of the assessment.

Response assessment is detailed in [Table 7](#).

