- a Evaluation: Screening assessments to be performed prior to first IMP administration unless otherwise indicated. Baseline evaluations should be completed within 7 days prior to the first dose of IMP, except for tumor assessment that may be performed within 28 days prior to IMP administration, and unless specified otherwise. There is no need to perform Cycle 1 Day 1 laboratory assessments that have been performed as part of screening within 3 days prior to first IMP administration. During the study treatment period, all assessments must be performed, and results should be reviewed by the investigator **prior to IMP administration** at that visit. After Cycle 1, samples for laboratory assessments (excluding PK & biomarker) can be collected up to 3 days prior to IMP administration. ICF must be signed before any study-specific procedures are performed and can be signed more than 28 days prior to first IMP administration. Screening time indicates the maximum time frame relative to the first IMP administration in which study procedures used to support eligibility are done.
- b Cycle: A treatment cycle is 21 days. See details in [Section 6.1](#) for IMP administration. If treatment cycles are adjusted, all procedures except tumor assessment imaging will be completed according to the Cycle number. Tumor assessment imaging will be performed at fixed time points from C1D1 regardless of any treatment delays.
- c Observation Period: Participants who enter the Observation period will be followed differently depending on the reason leading to permanent study treatment discontinuation. See Section 4.1 of the master protocol. For participant's convenience, all Follow-up assessments may occur during the same visit as that when tumor assessment is performed.
- d Survival Phone Call Follow-Up Period: Once the participant stops the tumor assessments due to PD or starts a new antineoplastic therapy, the participant moves into the Survival Follow-up Period and should be contacted by telephone approximately every 3 months \pm 14 days to assess for survival status. Updated survival status may be requested by the Sponsor at any time during the study.
- e Visits on C1D2, D3 are for safety-run in participants only.
- f Study Board may decide to cancel safety assessment on C1D15, upon agreement with Sponsor, if safety data justify it.

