3.2.2 Main analytical approach

The primary endpoints, CRR and ORR, will be analyzed with estimand 1 introduced in [Section 1.2.1](#). These endpoints are defined according to the following attributes:

- The endpoint complete response (CR) for cohort A
- The endpoint objective response (CR or PR) for cohort C1
- The treatment condition is SAR444245
 - in combination with pembrolizumab for Cohort A
 - in monotherapy for Cohort C1
- The analysis population is the efficacy population
- Intercurrent events (IE):
 - The new anticancer therapy IE will be handled with the “while not initiating new anti-cancer therapy” strategy; the primary endpoints will be assessed based on tumor assessments up to the time of new anticancer therapy.
 - The early IMP discontinuation IE will be handled with the “treatment policy” strategy; the primary endpoints will be assessed based on tumor assessments irrespective of the IMP discontinuation.

Population-level summary: Will include the - CRR (cohort A) and ORR (cohort C) and corresponding confidence interval using the Clopper Pearson exact method.

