3.3.1 Efficacy secondary endpoint(s)

3.3.1.1 *Definition of endpoint(s)*

The secondary efficacy endpoints are:

- The ORR is defined as the proportion of participants who have a CR or PR as BOR, for cohort A.
- The CRR is defined as the proportion of participants who have a CR as BOR, for cohort C1.
- The TTR is defined as the time from the first administration of IMP to the first tumor assessment at which the overall response was recorded as PR or CR determined by Investigator.

- The duration of response (DoR) is defined as the time from the first tumor assessment at which the overall response was recorded as PR or CR until progressive disease (PD) determined by Investigator, or death from any cause, whichever occurs first.
- The clinical benefit rate (CBR) is defined as the proportion of participants with clinical benefit (CR or PR as BOR, or SD lasting at least 6 months (i.e., 26 weeks or later from first IMP intake, allowing for the ± 7 days visit window for tumor assessment scheduled at 27 weeks) determined by Investigator per Lugano response criteria 2014.
- Progression free survival (PFS) defined as the time from the date of first IMP administration to the date of the first documented disease progression determined by Investigator or death due to any cause, whichever occurs first.

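### Tumor imaging after stopping treatment without PD is timed by two different clocks, and before Week 45 two SAP rules fit only one of them

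*Protocol*

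**What the plan says.** **Clock 1, from last IMP.** Master protocol Section 4.1 and the synopsis say that participants who stop or complete treatment without PD "will be followed every 3 months" (±7 days), counted from last IMP. This covers safety and "tumor imaging assessments, until PD, start of another anticancer therapy, final cohort cut-off, whichever comes first".

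**Clock 2, from first IMP.** Section 8.1.1 says "On study imaging will be performed every 9 weeks" (63 ± 7 days) after first IMP, and adds: "Imaging studies should follow calendar days and should not be adjusted for delays in cycle starts or extension". The CT/MRI row of Table 4 reads "Every 9 weeks and if clinically indicated until Week 45, and every 12 weeks from Week 45 until progressive disease". SoA footnote b in both substudies says "Tumor assessment imaging will be performed at fixed time points from C1D1 regardless of any treatment delays", and footnote q repeats the Section 8.1.1 calendar.

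**The SoA carries both.** Its CT/MRI row is marked at EOT and at the follow-up visits, whose column headings count mainly from last IMP. Footnote q on the same row counts from first IMP. Footnote c only allows follow-up assessments to share a visit with a tumor assessment.

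**The SAP.** For early IMP discontinuation, Section 3.2.2 says "the primary endpoints will be assessed based on tumor assessments irrespective of the IMP discontinuation". Section 3.3.1.2 applies the same treatment-policy strategy to DoR and PFS. CBR (Section 3.3.1.1) requires CR, PR, or SD at 26 weeks or later, a threshold set by the "visit window for tumor assessment scheduled at 27 weeks". Under Table 5, footnote c, a gap strictly longer than 20 weeks between evaluable assessments counts as two missed. A PD or death straight after such a gap is censored at the last evaluable scan.

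**The concern.** A site can follow either text and believe it is compliant. If the 3-month clock is applied, the schedule on which response and progression are observed changes at the moment treatment stops. A treatment-policy estimand is meant to be indifferent to that event.

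Two SAP rules look as though they were derived from the 9-week calendar: the 26-week CBR threshold and the 20-week missed-scan limit. If so, on the 3-month clock the same disease course could be classified differently for CBR, or counted as an event in one participant and censored in another, depending only on treatment status. Each cohort has 25 participants, so one reclassification moves CBR by 1/25 = 4 percentage points.

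**Working it through.** **Inputs.** 1 month = 30.4375 days (the SAP's convention), so 3 months = 91.3 days = 13.04 weeks. EOT = last IMP + 30 days = 4.29 weeks. Calendar scans: Weeks 9, 18, 27, 36, 45, 57 and so on. Weeks count from first IMP, and dates are nominal unless stated.

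**Reproducing the SAP's figures.**
- CBR threshold: 3 × 9 − 1 = 26 weeks, as stated.
- Missed-scan limit: 2 × 9 + 2 × 1 = 20 weeks, as stated.

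Both follow from 9-week scans with a 1-week window.

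**CBR on the 3-month clock.** With last IMP at Week 12:
- EOT: 12 + 4.29 = 16.3
- Follow-up 1: 12 + 13.04 = 25.0
- Follow-up 2: 12 + 26.09 = 38.1

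Week 25.0 is short of 26, so the first qualifying scan is Week 38.1. (Follow-up 1 on the last day of its window, 25.04 + 1 = 26.04, would just qualify.) With last IMP at Week 9 the scans are 13.3, 22.0 and 35.1, and no window rescues Week 22. The first scan at 26 weeks or later, EOT scan included, is:

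| Last IMP (week) | 3 | 6 | 9 | 12 | 15 | 18 | 21 | 24 |
|---|---|---|---|---|---|---|---|---|
| 3-month clock | 29.1 | 32.1 | 35.1 | 38.1 | 28.0 | 31.0 | 34.0 | 28.3 |
| Calendar | 27 | 27 | 27 | 27 | 27 | 27 | 27 | 27 |

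The lag runs from 1.0 to 11.1 weeks. The participants at risk of reclassification are those whose SD ends between Week 27 and the later scan. For example, with last IMP at Week 9 and progression at Week 30, the calendar has SD at Week 27, while the 3-month clock has its last SD at Week 22.

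**Missed-scan rule, one scan missed.**
- 9-week calendar: 18 weeks, at most 20 with windows. Not strictly over 20, so a following PD counts.
- 3-month clock, between follow-up visits: 2 × 13.04 = 26.1 weeks. Over 20, so PD is censored.
- 3-month clock, Follow-up 1 missed after an EOT scan: 26.09 − 4.29 = 21.8 weeks. Also over 20.

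Footnote c defines the gap between two scans that were done. If the same limit is counted to a date of death, a death more than 20 weeks after the last scan is censored, and on the 3-month clock that can happen after one missed scan.

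**Detection delay, last IMP at Week 9.** Mean delay with uniform progression times = Σ(interval²) / (2 × Σ interval).
- Calendar, 9-week intervals: 4.5 weeks.
- 3-month clock, intervals 4.29, 8.75, 13.04, 13.04: 435 / (2 × 39.1) = 5.6 weeks.

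The increase is about 1 week.

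**Simulation under assumed inputs.** Exponential PFS with median 4, 9 or 14.7 months (4 and 14.7 are within the figures in Section 2.2.1); 20% or 40% stop without PD, last dose at Weeks 3 to 27; EOT scan always done. Among participants progressing off treatment, 56% to 58% are detected later on the 3-month clock, with 0.6 to 0.9 weeks extra mean delay. Overall median PFS moves by 0 to 1 week.

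**After Week 45.** The intervals are 12 and 13.04 weeks. One missed 12-week scan leaves 24 weeks, also over 20, so both clocks censor.

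**The case against.** The best defense is sequential: 9-weekly imaging during treatment, 3-monthly in the observation period. That is workable, and footnotes b and c could also be read as keeping imaging on its own calendar. A reader might therefore infer that no site can comply; the documents show two usable readings with no rule for choosing. The sequential reading is also not what the text says. Section 8.1.1 calls the calendar on-study imaging, reserves on-treatment for the PET requirement, and Table 4 runs to PD rather than to EOT. Even if adopted, it leaves the two SAP rules misfitting.

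Several stronger inferences are tempting and not supported:
- *Participants who stop are scanned later and less often throughout.* The SoA marks CT/MRI at EOT. With last IMP at Week 9 the first off-treatment scan is at Week 13.3, before the calendar's Week 18, and each clock has given four scans by about Week 48.
- *No Week 27 scan can exist on the 3-month clock.* In Cohort C1 a last dose at Week 14 puts Follow-up 1 at Week 27.0, anyone stopping after Week 27 should already have that scan, and any later SD scan also qualifies.
- *CBR contradicts its estimand.* SAP Table 3 gives CBR none; its problem is the Week 27 anchor.
- *A late CR would be lost.* Off-treatment imaging continues to PD, new therapy or final cut-off, and the primary objective is updated at 3 years from LPI. A durable CR would be found later, not shown to be missed.

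Clinical suspicion of progression also triggers prompt imaging, which further limits delay. All intervals are descriptive, and only participants who stop early without PD and start no new therapy are materially affected.

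**Conclusion.** The inconsistency stands and should be resolved. The master protocol gives two imaging clocks after stopping without PD, and no text says which governs. If the 3-month clock is applied, assessment timing depends on treatment status while the SAP handles discontinuation by treatment policy for CR/OR, DoR and PFS.

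The consequences that matter arise before Week 45. CBR status can turn on the clock, by an amount that depends on the week of last dose. One missed 3-monthly scan can censor a progression that the 9-week calendar would count. A reader might infer a material bias in PFS; the calculations do not support that once the EOT scan is counted. Participants who complete all cycles (last dose at Week 102 in both cohorts) are barely affected.

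These sizes rest on nominal visit dates, an EOT scan being done, and, for the simulation, the assumed PFS and discontinuation inputs. The documents give no expected rate of stopping without PD, so the number of participants affected cannot be stated.

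**What to change.** In Section 4.1, the synopsis and the SoA observation-period columns, keep the 3-monthly visits for safety. State that tumor imaging stays on the Section 8.1.1 calendar from C1D1 until PD, new anticancer therapy or final cohort cut-off, whether or not treatment has stopped. Say whether the EOT scan is kept in addition.

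The 26-week CBR threshold and the 20-week limit then fit all participants up to Week 45 without change. The 24-week gap after one missed 12-week scan remains, and needs its own decision in SAP Table 5.

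The alternative is to state a switch to 3-monthly imaging at EOT and rewrite both SAP rules. That would reconcile the text but leave scan timing dependent on treatment status.

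The cost is protocol wording and one or two more CTs, which Table 4 already calls for, per participant who stops without PD before Week 45. With last IMP at Week 9, the calendar gives four scans by Week 45 (five if the EOT scan is kept), against three on the 3-month clock.

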8.3.1 Time period and frequency for collecting AE and SAE information

All AEs, including adverse events of new onset, as well as worsening of baseline signs and symptoms will be collected throughout study period, from the signing of the informed consent form (ICF) until **30 days** following cessation of study treatment.

All SAEs and AESIs will be collected throughout the study period, from the signing of the informed consent form (ICF) until **3 months** following last administration of study treatment.

All SAEs and AESI will be recorded and reported to the Sponsor or designee immediately and under no circumstance should this exceed 24 hours, as indicated in Appendix 3 ([Section 10.3](#)). The Investigator will submit any updated SAE data to the Sponsor within 24 hours of it being available.

Investigators are not obligated to actively seek information on AEs or SAEs after conclusion of the study participation. However, if the Investigator learns of any SAE, including a death, at any time after a participant has been discharged from the study, and he/she considers the event to be reasonably related to the study intervention or study participation, the Investigator must promptly notify the Sponsor.

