8.3.5 Pregnancy

- Details of all pregnancies in female participants and female partners of male participants will be collected after the start of study intervention and until 120 days (or refer to the individual substudy protocol) following cessation of study treatment, or 30 days following cessation of study treatment if the participant initiates another anticancer therapy
- If a pregnancy is reported, the Investigator will record pregnancy information on the appropriate form and submit it to the Sponsor within 24 hours of learning of the female participant or female partner of male participant (after obtaining the necessary signed informed consent from the female partner) pregnancy.
- Abnormal pregnancy outcomes (eg, spontaneous abortion, fetal death, stillbirth, congenital anomalies, ectopic pregnancy) are considered SAEs and will be reported as such.
- The participant /pregnant female partner will be followed to determine the outcome of the pregnancy. The Investigator will collect follow-up information on the participant /pregnant female partner and the neonate, and the information will be forwarded to the Sponsor.
- Any post-study pregnancy-related SAE considered reasonably related to the study intervention by the Investigator will be reported to the Sponsor as described in [Section 8.3.4](#). While the Investigator is not obligated to actively seek this information in former study participants /pregnant female partner, he or she may learn of an SAE through spontaneous reporting.
- Any female participant who becomes pregnant while participating in the study will discontinue study intervention.

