- a Blood Chemistry/hematology should be done with an overnight fasting if possible (should not interfere with hydration requirements). It will be performed weekly on D1 pre-dose, D8 and D15 (D15 for participants who receive Q3W only) during Cycle 1, then on Day 1 of every cycle up to Cycle 12, then every other cycle during Treatment Phase. Visits and assessments on C1D2-D3 will be performed for participants in the safety run-in or participants who are hospitalized because of high tumor burden or at Investigator's discretion. During the Observation Period, it will be performed at Follow-Up Visit 1. It can also be performed as clinically indicated. In case of Grade ≥ 3 liver function abnormal tests, additional tests will be repeated every 2-3 days until recovery to baseline value.
- b Modification of Diet in Renal Disease (MDRD) equation: Glomerular filtration rate (mL/min/1.73 m²) = 175 × (Serum Creatinine)-1.154 × (Age)-0.203 × (0.742 if Female) × (1.212 if African American)
- c Bicarbonate or carbon dioxide (venous) (if bicarbonate or carbon dioxide are assessed only on arterial blood at site level, to be done only if clinically indicated)
- d Endocrine function tests will be performed every 2 cycles throughout the entire treatment period and at EOT. During the Observation Period, they will be performed at Follow-Up Visit 1. They can also be performed as clinically indicated.
- e Pregnancy Test: Women of childbearing potential must have a negative urine pregnancy test result within 72 hours prior to first IMP administration of each cycle, at EOT and every 30 (± 7) days until 120 days (or refer to the individual substudy protocol) after the last dose of study treatment. If urine pregnancy results cannot be confirmed as negative, a serum pregnancy test will be required. Pregnancy tests (serum and/or urine tests) should be repeated if required by local guidelines.

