8.3 ADVERSE EVENTS (AES), SERIOUS ADVERSE EVENTS (SAES) AND OTHER SAFETY REPORTING

Please refer to the master protocol.

8.3.1 Time period and frequency for collecting AE and SAE information.

Please refer to the master protocol for AEs and SAEs collection. For participants in Cohort A, irAEs will be collected until 3 months following last administration of study treatment regardless of whether or not another anticancer therapy is initiated.

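### Participants who stop without PD can lose the 3-month safety visit, although SAEs, AESIs and (Cohort A) irAEs must still be collected to 3 months

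*Protocol*

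**What the plan says.** **Visits.** Section 4.1 of the master protocol splits follow-up by the reason for ending treatment.

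- Item 1 covers participants who stop, or complete the maximum cycles, without PD. They have safety and imaging visits every 3 months from the last dose, "until PD, start of another anticancer therapy, final cohort cut-off, whichever comes first, before moving to the Survival Phone Call Follow-Up Period". The telephone contacts that follow are made "to assess for survival status".
- Item 2 covers participants who stop with PD. They "will be followed for safety in the Follow-Up Visit 1", 3 months after the last dose, before the calls begin. New therapy does not cancel that visit.

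The synopsis carries the same two items. Footnote d of the SoA, in both substudies, says: "Once the participant stops the tumor assessments due to PD or starts a new antineoplastic therapy, the participant moves into the Survival Follow-up Period".

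**Collection.** Master protocol Section 8.3.1: "All SAEs and AESIs will be collected throughout the study period, from the signing of the informed consent form (ICF) until" 3 months after the last administration. It makes no exception for PD or new therapy. For Cohort A, Substudy 01 Section 8.3.1 adds that "irAEs will be collected until 3 months following last administration of study treatment regardless of whether or not another anticancer therapy is initiated".

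**Content of the visit.** On chemistry and hematology, Table 6 footnote a (Section 10.2) states: "During the Observation Period, it will be performed at Follow-Up Visit 1". Footnote d of that table places the endocrine tests there too.

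**Pregnancy.** Section 8.3.8 lists pregnancy as an AESI. Section 8.3.5 collects pregnancies to 120 days (or as the substudy states), "or 30 days following cessation of study treatment if the participant initiates another anticancer therapy".

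**The concern.** The visit schedule and the collection window do not match for one group: participants who stopped without PD and then progress, or start another therapy, before Follow-Up Visit 1. Their events are still to be collected, but the schedule no longer provides an occasion to find new ones.

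The visit matters because some of the events are defined by laboratory values. The liver AESI in Section 8.3.8 is a transaminase, bilirubin and alkaline phosphatase combination. Thyroid and other endocrine irAEs are found through the endocrine panel. Any irAE of Grade 3 or above is an AESI in both cohorts. Substudy 01 Section 6.5.4.4 itself warns that irAEs may appear several months after the last pembrolizumab dose. A survival call performs no test and is not described as asking about adverse events.

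The group includes participants who stopped for toxicity, in whom late events are of particular interest. Participants who stopped with PD keep the visit, and no reason is given for the difference. Safety is a secondary objective, and with 25 participants per cohort one missed participant with an event is 1/25 = 4 percentage points.

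**Working it through.** **1. The rules side by side, for a participant with PD or new therapy between the EOT visit and month 3**

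| Rule | Stopped without PD | Stopped with PD |
|---|---|---|
| Section 4.1 and synopsis | moves to survival calls at that event | Follow-Up Visit 1 kept |
| SoA footnote d | moves to survival follow-up | read alone, the same, which conflicts with item 2 |
| Section 8.3.1 (SAE, AESI) | collect to 3 months | collect to 3 months |
| Substudy 01 Section 8.3.1 (irAE, Cohort A) | collect to 3 months | collect to 3 months |

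The amendment summary says that the stop of AE and SAE collection at new therapy was removed from Section 8.3.1. Section 4.1 item 1 still ends the visits at that event.

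**2. Length of the gap**

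Inputs: EOT visit at 30 ± 7 days after the last dose (Section 4.1); collection window of 3 months (Section 8.3.1); 30.4375 days per month (the SAP's conversion, Section 3.6.1).

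- Window: 3 × 30.4375 = 91.3 days.
- EOT at day 30: 91.3 − 30 = 61.3 days, 67% of the window.
- EOT at day 23: 91.3 − 23 = 68.3 days, 75%.
- EOT at day 37: 91.3 − 37 = 54.3 days, 59%.

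The EOT visit may also be brought forward to precede further therapy. The gap is then longer and can reach into the 30-day treatment-emergent period. A participant with neither PD nor new therapy by 3 months has no gap.

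**3. The plan's own safety figure, reproduced**

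Section 9.2 of each substudy gives the chance of seeing at least one case of an AE among 25 participants: 1 − (1 − p)^25.

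- p = 1%: 0.2222 (stated 22.2%).
- p = 2%: 0.3965 (stated 39.7%).
- p = 5%: 0.7226 (stated 72.3%).

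All three agree.

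**4. Illustration only**

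The documents give no rate of early exit to phone calls. Assume that k of 25 exit, that the AE in question arises only after the EOT visit with true incidence 5%, and that a share c of such events is still captured in those k. The detection probability is 1 − 0.95^(25 − k) × (1 − 0.05c)^k.

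| k | c = 0 | c = 0.5 |
|---|---|---|
| 0 | 72.3% | 72.3% |
| 2 | 69.3% | 70.8% |
| 5 | 64.2% | 68.4% |
| 10 | 53.7% | 64.0% |

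The table shows how the stated 72.3% would respond. It does not estimate what will happen.

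**The case against.** The strongest reply is that a visit schedule and a reporting window are different things. Section 8.3.1 still requires collection to 3 months, and it lifts the duty to seek events actively only after study participation ends. Survival follow-up is part of participation. This stands: a reader might infer that late toxicity *is* under-ascertained, or that the reported incidence *is* biased downward, but nothing in the documents says that these events go uncollected.

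Sections 7.1.1, 7.1.1.1 and 8.3.3 also follow adverse events to resolution or stabilization. That covers events already known, or defers to the same schedule. It does not find new ones, and Section 8.3.3 ends further follow-up of AEs above Grade 1 at a new antineoplastic therapy if that comes first.

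Women of childbearing potential have pregnancy tests every 30 days after treatment (Section 8.2.5), for 120 days or as the substudy states, so some do have a scheduled contact. The contact carries a pregnancy test, not the chemistry, hematology or endocrine panels.

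The effect on the secondary objective is limited. TEAEs end 30 days after the last dose and are the main AE analysis, and the laboratory analyses use on-treatment values. No contrast by reason for stopping is planned. This also stands.

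PD found at the Follow-Up Visit 1 scan costs nothing, because the visit has then taken place. Only earlier PD or earlier new therapy opens the gap. Finally, the AE/SAE row of the SoA cannot be read reliably in the available text, so it does not settle at which post-treatment visit AEs are assessed.

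**Conclusion.** The mismatch is real and should be corrected. For participants who stopped or completed without PD, and whose PD or new therapy precedes Follow-Up Visit 1, about 61 of the 91 days of required collection (54 to 68) have no scheduled safety visit or safety laboratory test. This rests on an EOT visit at 30 ± 7 days and on following Section 4.1 item 1 and footnote d as written.

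The consequence is a risk that new-onset late SAEs, AESIs and, in Cohort A, irAEs are missed. It bears mainly on the descriptive post-treatment AE, SAE and AESI summaries, and reaches TEAEs only if the EOT visit is brought forward before day 30.

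Three wider readings are not supported:

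- It does not affect everyone who stops without PD.
- The explicit irAE clause is in Substudy 01 and covers Cohort A only. Cohort C1 has the SAE and AESI window, which does include irAEs of Grade 3 or above.
- No percentage of participants affected can be given, because the documents state neither how many stop without PD nor how soon they progress or change therapy.

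The pregnancy rules contradict each other separately: as an AESI, pregnancy is collected to 3 months, yet Section 8.3.5 stops at 30 days once new therapy begins.

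**What to change.** In Section 4.1 item 1, the synopsis and SoA footnote d of both substudies, state that the Follow-Up Visit 1 safety assessment, 3 months after the last dose, is done for every participant regardless of PD or new anticancer therapy, and that only imaging stops at those events. This brings item 1 and footnote d into line with item 2 and Section 8.3.1.

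Separately, reconcile the 30-day stop at new therapy in Section 8.3.5 with the 3-month AESI window in Section 8.3.1. Do this without shortening the 120-day default: simply setting Section 8.3.5 to the AESI period would cut pregnancy collection for participants who start no new therapy.

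The cost is wording in these places and one already planned visit for what is likely to be a few participants, some of whom will by then be on another therapy. Events found at that visit may be harder to attribute, so the start date of the new therapy should be shown beside them.
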